3.1 Study design

Japanese patients are allowed to enter this extension study after completion of Epoch 4 (an open-label treatment epoch) in CACZ885N2301 study. This study consists of two study epochs (Screening epoch and Extension-treatment epoch). This study will be continued until approval in Japan or the discontinuation of the development of the drug in Periodic Fever Syndromes.

In this study, all patients will receive the same dose and regimen as administered at the end of study CACZ885N2301 consisting of 1 or 2 subcutaneous injections every 4 or 8 weeks. Safety will be evaluated every 8 weeks.

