5.6 Study completion and discontinuation

5.6.1 Study completion and post-study treatment

A patient will be considered to have completed the study when the patient has completed the last visit of extension- treatment epoch planned in the protocol.

For all patients a safety follow-up visit should be conducted (e.g. by telephone) 30 days after last visit 199 or TD/PSW, or 8 weeks after last injection of investigational drug, whichever is later. The investigator must provide follow-up medical care for all patients who are prematurely withdrawn from the study, or must refer them for appropriate ongoing care. This care does not require any special treatment but it is recommended not to initiate any live vaccination or biologic treatment until 3 months after the last dose of study treatment.

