5.6.2 Discontinuation of study treatment

Discontinuation of study treatment for a patient occurs when study drug is stopped earlier than the protocol planned duration, and can be initiated by either the patient or the investigator.

The investigator must discontinue study treatment for a given patient if, on balance, he/she believes that continuation would negatively impact the risk/benefit of trial participation.

Study treatment must be discontinued under the following circumstances:

- Emergence of the following adverse events:
 - a. Absolute QTcF > 500 msec, confirmed by repeat electrocardiogram (ECG) measurements
 - b. Serious infections combined with neutropenia Common Toxicity Criteria (CTC) grades ≥ 1 (ANC < $2.0 \times 10^9/L$)
 - c. CKD as per NKF stages ≥ 4 : eGFR ≤ 29 mL/min/1.73 m²
 - d. Confirmed diagnosis of latent or active Tuberculosis
 - e. Onset of any malignancy
- Any of the following laboratory abnormalities:
 - a. Neutropenia CTC Grades ≥ 2 : ANC < $1.5 \times 10^9/L$
 - b. Thrombocytopenia CTC Grade 4: Platelets < $10.0 \times 10^9/L$
- Pregnancy
- Use of prohibited treatment as per [Table 5-1](#)
- Any other protocol deviation that results in a significant risk to the patient's safety

If discontinuation of study treatment occurs, the patient should NOT be considered withdrawn from the study. The patient should return to the clinic as soon as possible, after discontinuation of study drug, for a study treatment discontinuation visit. Treatment discontinuation visit assessments detailed in the "treatment discontinuation visit" in [Table 6-1](#) should be completed and recorded in the eCRF. The investigator must determine the primary reason for the patient's premature discontinuation of study treatment and record this information on the Dosage Administration eCRF.

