5.6.5 Early study termination by the sponsor

The study can be terminated by Novartis at any time for any reason. This may include reasons related to the benefit risk assessment of participating in the study, practical reasons, or for regulatory or medical reasons (including slow enrolment). Should this be necessary, the patient must be seen as soon as possible and treated as a prematurely withdrawn patient. The investigator may be informed of additional procedures to be followed in order to ensure that adequate consideration is given to the protection of the patient's interests. The investigator will be responsible for informing the Institutional Review Board/Independent Ethics Committee (IRBs/IECs) of the early termination of the trial.

6 Visit schedule and assessments

Table 6-1 lists all of the assessments and indicates with an "x" when the visits are performed.

At a minimum, patients will be contacted for safety evaluations and a follow-up visit or phone call for Serious Adverse Event (SAE) must be performed 30 days following study TD, premature subject withdrawal (PSW) or 8 weeks after last injection of study drug, whichever is later.

Documentation of attempts to contact the patient should be recorded in the patient record.

Table 6-1 Assessment schedule

Epoch	Screening (Epoch 1)	Extension- treatment (Epoch 2)			Safety follow-up
	1#	101#	102, 103....	199 and TD and/or PSW ⁶	
Week (Relative to Baseline of core study)	113	113	121, 129....		
Day	785	785	841, 897....		PSW +30 or 8 weeks after last injection
Informed consent	X				
Demography	X				
Inclusion/Exclusion Criteria	X				
Relevant medical history/ current medical conditions	X				
Prior and concomitant medications (including vaccination status) *	X	X	X	X	
Surgical and medical procedures*	X	X	X	X	
Disease Diagnosis	X				
Disease characteristics	X				
Pregnancy test –urinalysis (for females of child bearing potential) *		S		S	
Physical examination ^{*,7}		S	S	S	
Weight ^{2,3,7}		S	S		
PGA ^{2,4,7}		S	S		
Hematology (local Lab) *		X	X	X	
Blood chemistry (local Lab) *		X	X	X	
CRP (local Lab) ^{2,5,7}		S	S		
Administration of open-label treatment ¹		X	X		
Adverse events*	X	X	X	X	
Local tolerability ^{*,7}		S	S	S	
Screening phase disposition form	X				
Study phase completion form*				X	
Follow-up visit or phone call for SAEs*					S

TD = Study treatment discontinuation; PSW = Premature subject withdrawal

X = assessment to be recorded on clinical data base

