S = assessment to be recorded on source documentation only

*These assessments are also to be conducted for patients who discontinue

Visit 1 of this extension study and Visit 399 of the CACZ885N2301 study are conducted on the same day. Visit 1 and Visit 101 can be on the same day

1. Patients receiving ACZ885 q4w or up-titrated to q4w administration will come back every 4 weeks for unscheduled visits at Day 813, Day 869 and so forth in addition to the scheduled visits

2. These assessments are source documentation only and will not be entered into the CRF, because they will be used only for dose adjustment or judgement of up-titration due to flare. Flare is defined as simultaneous occurrence of a clinical flare and a serological flare defined as follows:

- PGA \geq 2 (clinical flare)

- CRP \geq 30 mg/L (serological flare)

3. Body weight to the nearest 0.1 kilogram (kg) in indoor clothing, but without shoes

4. The PGA (physician's global assessment) will be based on a 5-point scale:

- 0 = None (no) disease associated clinical signs and symptoms

- 1 = Minimal disease associated signs and symptoms

- 2 = Mild disease associated signs and symptoms

- 3 = Moderate disease associated signs and symptoms

- 4 = Severe disease associated signs and symptoms

5. CRP will be measured at the local laboratory, including any unscheduled visits. CRP value will be standardized to a normal range of 0-10 mg/L.

6. After canakinumab is approved for Periodic Fever Syndromes (TRAPS, HIDS, or crFMF) in Japan, all subjects who continue study treatment at the timing will be expected to perform V199 evaluation approximately 8 weeks after their most recent assessment visit, and then will enter the safety follow-up period.

7. If V 101 of this extension study and V 399 of the CACZ885N2301 study are conducted on the same day, Physical exam, PGA, CRP, weight, local tolerability will be assessed only one time.

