7.1 Adverse events

An adverse event (AE) is any untoward medical occurrence (e.g., any unfavorable and unintended sign [including abnormal laboratory findings], symptom or disease) in a subject or clinical investigation subject *after providing written informed consent* for participation in the study until the end of study visit. Therefore, an AE may or may not be temporally or causally associated with the use of a medicinal (investigational) product.

In addition, all reports of intentional misuse and abuse of the product are also considered an adverse event irrespective if a clinical event has occurred.

The occurrence of adverse events must be sought by non-directive questioning of the patient at each visit during the study. Adverse events also may be detected when they are volunteered by the patient during or between visits or through physical examination findings, laboratory test findings, or other assessments.

Abnormal laboratory values or test results constitute adverse events only if they fulfill at least one of the following criteria:

- they induce clinical signs or symptoms,
- they are considered clinically significant,
- they require therapy.

Clinically significant abnormal laboratory values or test results must be identified through a review of values outside of normal ranges/clinically notable ranges, significant changes from baseline or the previous visit, or values which are considered to be non-typical in patient with underlying disease. Investigators have the responsibility for managing the safety of individual patient and identifying adverse events. Alert ranges for laboratory and other test abnormalities are included in [Appendix 1](#).

Adverse events must be recorded in the Adverse Events CRF under the signs, symptoms or diagnosis associated with them, accompanied by the following information:

- the severity grade
 - a. mild: usually transient in nature and generally not interfering with normal activities
 - b. moderate: sufficiently discomforting to interfere with normal activities
 - c. severe: prevents normal activities
- its relationship to the study treatment
 - Yes
 - No
- its duration (start and end dates) or if the event is ongoing an outcome of not recovered/not resolved must be reported.
- whether it constitutes a serious adverse event (SAE - See [Section 7.2](#) for definition of SAE) and which seriousness criteria have been met.
- action taken regarding [investigational] treatment

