2.8.1 Adverse events (AEs)

A listing will be presented to display individual adverse events reported in Epoch 1 and 2.

Also, SAEs will be listed.

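### After early discontinuation, new non-serious AEs in the rest of the last dosing interval can be missing from the primary listing, because the only later contact is SAE-only and outside Epochs 1 and 2

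*Protocol*

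**What the plan says.** Protocol 5.6.2 sets no minimum time between the last injection and the TD visit: "The patient should return to the clinic as soon as possible, after discontinuation of study drug, for a study treatment discontinuation visit". It also says that such a patient does not count as withdrawn.

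Protocol 5.6.1 then sets a safety contact at "30 days after last visit 199 or TD/PSW, or 8 weeks after last injection of investigational drug, whichever is later". Section 3.1.2 times it from TD in the same way. In Table 6-1 the AE row is marked for database entry at Visit 1, Visit 101, Visits 102 onward and the shared V199/TD/PSW column. It is blank under Safety follow-up. The only row marked in that column is "Follow-up visit or phone call for SAEs", and its code is defined as "S = assessment to be recorded on source documentation only".

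SAP 2.8.1 sets the scope of the primary output: "A listing will be presented to display individual adverse events reported in Epoch 1 and 2". Protocol 3.1 gives the study only those two epochs, screening and extension treatment. Footnote 6 to Table 6-1 places the safety follow-up after V199: patients still on treatment at approval are to "perform V199 evaluation approximately 8 weeks after their most recent assessment visit, and then will enter the safety follow-up period".

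Protocol 7.1 counts AEs from written consent "for participation in the study until the end of study visit". That visit is not defined.

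**The concern.** AEs are the only primary variable, and the report consists of individual listings without summaries. The value of the listing therefore depends on how completely each patient's events are entered.

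A TD visit held promptly can fall early in a dosing interval. Take two patients on 8-weekly dosing who each have a new non-serious AE five weeks after an injection. If the first stays on drug, the event is asked about at the next scheduled visit and listed. If the second had a TD visit at week 1, no later scheduled contact enters the event in the database, although it lies inside the same dosing interval. Patients who stop include those stopped because of an AE or a laboratory abnormality, for whom a complete account matters most.

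**Working it through.** **Inputs.** Dosing every 28 or 56 days (Protocol 3.1). Safety contact at the later of TD + 30 days and last injection + 56 days (Protocol 3.1.2, 5.6.1). At most 10 patients (Protocol 9.8). The time from last injection to TD is not given, so it is written as d days and a range is shown.

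**The plan's own schedule.** Day = (week − 1) × 7 + 1 gives Days 785, 841 and 897 for Weeks 113, 121 and 129, as in Table 6-1. Visits are 56 days apart. The additional 4-weekly visits fall on 785 + 28 = 813 and 841 + 28 = 869, also as stated.

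**Formulas, with the last injection as day 0.**
- Contact day = max(d + 30, 56).
- SAE-only window from TD to contact = max(30, 56 − d).
- Rest of the last dosing interval after TD = 56 − d (q8w) or 28 − d (q4w), not below 0.

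**Comparator.** A q8w patient on drug at approval has V199, with AE entry, about 56 days after the last assessment visit and injection. The contact is then on day max(56 + 30, 56) = 86. That patient has 0 uncovered days inside the dosing interval, but also has an SAE-only window of 86 − 56 = 30 days. The excess window for an early stopper is therefore max(30, 56 − d) − 30 = max(0, 26 − d).

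| d | Contact day | SAE-only window | Excess over completer | Rest of q8w interval | Rest of q4w interval |
|---|---|---|---|---|---|
| 0 | 56 | 56 | 26 | 56 (100%) | 28 (100%) |
| 7 | 56 | 49 | 19 | 49 (87.5%) | 21 (75%) |
| 14 | 56 | 42 | 12 | 42 (75%) | 14 (50%) |
| 26 | 56 | 30 | 0 | 30 (53.6%) | 2 (7.1%) |
| 28 | 58 | 30 | 0 | 28 (50%) | 0 |
| 56 | 86 | 30 | 0 | 0 | 0 |

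The two measures differ. At d = 28 on q8w dosing the stopper's window is no longer than the completer's, but it runs from day 28 to day 58 after the last injection instead of day 56 to day 86. Half of the dosing interval is then without routine AE entry.

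**Is any later visit with AE entry scheduled after TD?**
- Footnote 6 assigns the approval-time V199 to patients who are still being treated.
- Sections 3.1.2 and 5.6.1 time the safety contact directly from TD, and 5.6.1 names TD/PSW as an alternative to V199.
- The asterisk in Table 6-1, which extends rows to patients who discontinue, sits on exactly the rows marked in the V199/TD/PSW column plus the follow-up row. It fits a description of what is done at those contacts and does not establish continued 8-weekly visits.

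No such visit is scheduled.

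**The case against.** A reader might infer that AE collection stops at TD. The documents do not say so. Section 5.6.2 and footnote 2 to Table 5-1 keep the patient in the study, the latter with safety follow-up. Section 6.5 makes its assessments mandatory after permanent discontinuation. Section 7.1 runs AE collection to an undefined end-of-study visit, which could be read as V199. The column heading in Table 6-1 allows TD and a later V199 for the same patient. If a site brought a stopped patient back in Epoch 2, the AEs found would be listed. This stands: the loss is possible, not demonstrated. It does not remove the point, because no such return visit is scheduled and 6.5 covers physical examination, laboratory tests and pregnancy, not AE entry. If the end-of-study visit means the safety contact, 7.1 conflicts with Table 6-1 and SAP 2.8.1.

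A reader might also take the whole SAE-only window as the cost of stopping early. It is not, since completers have 30 such days after V199. Nor does the recommendation in footnote 1 to Table 5-1, to wait 3 months before live vaccines or another biologic, define an AE window.

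Finally, much is still captured. SAEs are reported, and the SAP lists them without an epoch limit. Detected AEs are followed to resolution or until judged permanent. Liver and renal events have their own follow-up with AE CRF entry. New AEs thought possibly related reach source documents, and Section 6 describes the contact as covering safety evaluations generally. An SAE-only last contact is a defensible choice in a continued-access study. All of this stands and limits the point to new non-serious AEs without those triggers.

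**Conclusion.** The point holds as a cheap improvement. On the schedule as written, new non-serious AEs after an early TD visit can be missing from the primary listing for up to 56 − d days of the last q8w interval or 28 − d days of the last q4w interval. The loss within the interval is nil if TD falls on a due-dose visit. The SAE-only window exceeds a q8w completer's by max(0, 26 − d) days.

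This rests on two assumptions: that TD is the patient's last visit with database entry, and that d is small enough to leave part of the interval open. Neither d nor a discontinuation rate is given, so the number affected is unknown, from 0 to 10. With at most 10 patients, each one affected is at least 10% of the study. The documents do not support concluding that safety follow-up after TD is absent, or that events have certainly been lost.

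**What to change.** For patients who stop drug before V199:

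1. In Table 6-1, mark the AE row X in the Safety follow-up column, so that all new AEs since TD are asked about and entered in the AE CRF.
2. In Protocol 5.6.2 and 7.1, state that AE collection runs at least to that contact (the later of TD + 30 days and last injection + 8 weeks). Word this as a minimum: it should not end participation there or weaken Section 6.5 or footnote 2 to Table 5-1, since that could shorten follow-up.
3. In SAP 2.8.1, list AEs from Epoch 1, Epoch 2 and safety follow-up, with days since last injection. SAP Table 2-1 already defines the last administration date.

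The contact falls on day max(d + 30, 56), never before day 56, so either dosing interval is covered in full. The SAE-only contact after V199 can stay as it is.

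The cost is one table cell, about two protocol sentences and one SAP phrase, a few more questions in a contact already required, and some extra AE entry for any of at most 10 patients. The protocol edits need a short written amendment approved under Section 11.1. No visits or laboratory tests are added, and the stopping rules do not change.

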5.6.3 Withdrawal of informed consent

Patients may voluntarily withdraw consent to participate in the study for any reason at any time. Withdrawal of consent from the study is defined as when a patient:

- Does not want to participate in the study anymore
- and
- Does not want any further visits or assessments

and

- Does not want any further study related contacts

and

- Does not allow analysis of already obtained biologic material

In this situation, the investigator must make every effort (e.g. telephone, e-mail, letter) to determine the primary reason for the patient's decision to withdraw his/her consent and record this information.

Study treatment must be discontinued and no further assessments conducted, and the data that would have been collected at subsequent visits will be considered missing.

Further attempts to contact the patient are not allowed unless safety findings require communicating or follow-up.

All efforts should be made to complete the assessments prior to study withdrawal. A final evaluation at the time of the patient's study withdrawal should be made as detailed in the assessment table.

5.6.4 Loss to follow-up

For patients whose status is unclear because they fail to appear for study visits without stating an intention to discontinue or withdraw, the investigator should show "due diligence" by contacting the patient, family or family physician as agreed in the informed consent and by documenting in the source documents steps taken to contact the patient, e.g. dates of telephone calls, registered letters, etc. A patient cannot be considered as lost to follow-up until the time point of his/her scheduled end of study visit would have occurred.

5.6.5 Early study termination by the sponsor

The study can be terminated by Novartis at any time for any reason. This may include reasons related to the benefit risk assessment of participating in the study, practical reasons, or for regulatory or medical reasons (including slow enrolment). Should this be necessary, the patient must be seen as soon as possible and treated as a prematurely withdrawn patient. The investigator may be informed of additional procedures to be followed in order to ensure that adequate consideration is given to the protection of the patient's interests. The investigator will be responsible for informing the Institutional Review Board/Independent Ethics Committee (IRBs/IECs) of the early termination of the trial.

6 Visit schedule and assessments

Table 6-1 lists all of the assessments and indicates with an "x" when the visits are performed.

At a minimum, patients will be contacted for safety evaluations and a follow-up visit or phone call for Serious Adverse Event (SAE) must be performed 30 days following study TD, premature subject withdrawal (PSW) or 8 weeks after last injection of study drug, whichever is later.

Documentation of attempts to contact the patient should be recorded in the patient record.

Table 6-1 Assessment schedule

Epoch	Screening (Epoch 1)	Extension- treatment (Epoch 2)			Safety follow-up
	1#	101#	102, 103....	199 and TD and/or PSW ⁶	
Week (Relative to Baseline of core study)	113	113	121, 129....		
Day	785	785	841, 897....		PSW +30 or 8 weeks after last injection
Informed consent	X				
Demography	X				
Inclusion/Exclusion Criteria	X				
Relevant medical history/ current medical conditions	X				
Prior and concomitant medications (including vaccination status) *	X	X	X	X	
Surgical and medical procedures*	X	X	X	X	
Disease Diagnosis	X				
Disease characteristics	X				
Pregnancy test –urinalysis (for females of child bearing potential) *		S		S	
Physical examination ^{*,7}		S	S	S	
Weight ^{2,3,7}		S	S		
PGA ^{2,4,7}		S	S		
Hematology (local Lab) *		X	X	X	
Blood chemistry (local Lab) *		X	X	X	
CRP (local Lab) ^{2,5,7}		S	S		
Administration of open-label treatment ¹		X	X		
Adverse events*	X	X	X	X	
Local tolerability ^{*,7}		S	S	S	
Screening phase disposition form	X				
Study phase completion form*				X	
Follow-up visit or phone call for SAEs*					S

TD = Study treatment discontinuation; PSW = Premature subject withdrawal

X = assessment to be recorded on clinical data base

S = assessment to be recorded on source documentation only

*These assessments are also to be conducted for patients who discontinue

Visit 1 of this extension study and Visit 399 of the CACZ885N2301 study are conducted on the same day. Visit 1 and Visit 101 can be on the same day

1. Patients receiving ACZ885 q4w or up-titrated to q4w administration will come back every 4 weeks for unscheduled visits at Day 813, Day 869 and so forth in addition to the scheduled visits

2. These assessments are source documentation only and will not be entered into the CRF, because they will be used only for dose adjustment or judgement of up-titration due to flare. Flare is defined as simultaneous occurrence of a clinical flare and a serological flare defined as follows:

- PGA \geq 2 (clinical flare)

- CRP \geq 30 mg/L (serological flare)

3. Body weight to the nearest 0.1 kilogram (kg) in indoor clothing, but without shoes

4. The PGA (physician's global assessment) will be based on a 5-point scale:

- 0 = None (no) disease associated clinical signs and symptoms

- 1 = Minimal disease associated signs and symptoms

- 2 = Mild disease associated signs and symptoms

- 3 = Moderate disease associated signs and symptoms

- 4 = Severe disease associated signs and symptoms

5. CRP will be measured at the local laboratory, including any unscheduled visits. CRP value will be standardized to a normal range of 0-10 mg/L.

6. After canakinumab is approved for Periodic Fever Syndromes (TRAPS, HIDS, or crFMF) in Japan, all subjects who continue study treatment at the timing will be expected to perform V199 evaluation approximately 8 weeks after their most recent assessment visit, and then will enter the safety follow-up period.

7. If V 101 of this extension study and V 399 of the CACZ885N2301 study are conducted on the same day, Physical exam, PGA, CRP, weight, local tolerability will be assessed only one time.

